4.3 Patient Withdrawal

Patients may withdraw from the study at any time at their own request without stating the reason(s) for withdrawal. If a patient withdraws early from the study after start of treatment an early termination (ET) visit should be arranged, preferably 7-14 days after the last dose of study drug.

"Non-naïve" patients (including "naïve" patients reclassified as "non-naïve") will be withdrawn from the study if their urine sample from **Visit 1** (Baseline 1) detects levels of N-Acetyl-D-Leucine above the permitted threshold.

The treating physician may decide that a patient should be withdrawn from the study or from the study drug. Reasons for withdrawal from the study or the study drug may include, but are not limited to, the following:

- Development of any adverse event (AE), serious AE (SAE), laboratory abnormality, condition, intercurrent illness, injury, medical condition, or use of a medication that is likely to interfere with patient safety, the overall assessment, or the study procedures, such that continued participation in the study would not be in the best interest of the patient.
- Consent withdrawal.
- The patient becomes pregnant or plans to become pregnant.
- Significant patient noncompliance, defined as an unwillingness to complete the procedures defined in the schedule of events.
- Patient lost to follow-up (i.e., staff unable to contact patient after several attempts).
- Investigator, Medical Monitor, and/or Sponsor decision for any other reason not listed above that may invalidate the results of the study or jeopardizes the health and/or safety of a patient
- Complications related to pandemics such as COVID-19.

Patients who discontinue study drug prior to completing the full treatment period, should be asked to complete the remaining study visits as far as possible and complete safety assessments at a minimum. If unwilling to complete the remaining study visits, regardless of the reason for withdrawal, best efforts should be made to have the patient take part in early termination (ET) procedures, preferably 7-14 days following the last dose of the study drug, unless the patient is

lost to follow-up or has withdrawn his/her consent to further study participation. Due to COVID-19, the ET visit may need to be postponed or conducted remotely, after discussion with the PI and the Sponsor.

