8 STATISTICAL METHODS

8.1 General Analysis Plan

8.1.1 Disposition of Patients

The number of patients enrolled, plus the numbers contained within the Safety Analysis Set (SAF), the intention-to-treat analysis set (ITT), the modified intention-to-treat analysis set (mITT) and the Per Protocol Set (PPS) will be summarized overall and by country. The number of patients discontinuing treatment, together with the primary reason for discontinuation will be presented.

Protocol Deviations

Protocol deviations include but are not limited to:

- Violation of key inclusion/exclusion criteria
- Use of Prohibited Medications
- Inadequate study medication compliance
- Urgent/ contingency measures implemented due to COVID-19, including delayed or missed assessments due to postponed or skipped in-person visits.

Further detail will be provided in the Statistical Analysis Plan (SAP)

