5.5.4 Disposition

A summary table will be created, stating the number of patients per site, including site number, location/country, and investigator.

To present disposition, a summary of all included, randomised, treated and completed patients will be created. Number/percentage screened will be included as well (if available in the database). Additionally, in the same summary, the number/percentage of patients in the SAF, mITT and PPS will be presented. Furthermore, the frequency and percentage per reason for non-completion will be added.

Additionally, a listing displaying all disposition information (including reasons for withdrawal and reasons for exclusion from the analysis population, if available electronically) on a per patient level will be created. This listing will include follow-up time for each patient, calculated from date of first dose until end of study for the Parent phase.

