5.7 Safety and tolerability evaluation

5.7.1 Adverse events

A treatment emergent adverse event (TEAE) is defined as an adverse event that appears during or after study treatment and was absent before.

Clinical Study Reference: IB1001-202

An AE overview table will be created displaying the number and percentage of subjects experiencing a treatment-emergent adverse event (TEAE) and the number of TEAEs for: any TEAE, any mild/moderate/severe TEAE, any related/unrelated TEAE, any serious AE, and any TEAE leading to study discontinuation.

Furthermore, all TEAEs will be tabulated by System Organ Class (SOC) and Preferred Terms (PTs) within each SOC according to the MedDRA terminology list, using frequency counts (number of subjects with at least one event, and number of events) and percentage of subjects with the event.

TEAEs will also be tabulated by severity (mild/moderate/severe) and by relationship to study medication (related/unrelated). Similar tables will be created for TEAEs leading to premature discontinuation, SAEs and deaths, if applicable. These summary tables will be presented by decreasing frequency of occurrence based on SOC and PT.

In addition, similar TEAE tables (overall, by severity and by relationship, premature discontinuation, SAEs, and deaths) by SOC and PT will be presented per treatment cycle, and frequencies and percentages will be determined for the active treatment cycle and the washout cycle. The treatment cycle is the period between start of first treatment at Visit 2 and 24 hours after last dose at Visit 4. The washout cycle starts 24 hours after last dose at Visit 4 until and including Visit 6.

The summary tables will be accompanied by individual subject listings of *all* AEs including information on AE number, actual AE description, date/time of start and end of AE (or ongoing), PT (MedDRA), SOC (MedDRA), severity, relationship, pre-dose (yes/no), seriousness, action taken, outcome and other information collected in the CRF for adverse events. Pre-dose AEs are not considered to be treatment-emergent, except in case of worsening during/after study treatment (to be collected as separate AE in the database). AEs starting prior to administration of the study drug will only be listed. In this listing, a clear distinction will be made between prior and treatment emergent events.

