14.3 Safety Data Summary figures and tables – 14.3.1 Displays of Adverse Events	
14.3.1.1	Overview adverse events
14.3.1.2	Treatment emergent adverse events
14.3.1.3	Treatment emergent adverse events by severity grade
14.3.1.4	Treatment emergent adverse events by relationship
14.3.1.5	Treatment emergent adverse events leading to premature discontinuation
14.3.1.6	Treatment emergent adverse events by treatment cycle
14.3.1.7	Treatment emergent adverse events by severity grade by treatment cycle
14.3.1.8	Treatment emergent adverse events by relationship by treatment cycle
14.3.1.9	Treatment emergent adverse events leading to premature discontinuation by treatment cycle
14.3 Safety Data Summary figures and tables – 14.3.2 Listings of Deaths, Other Serious and Significant Adverse Events	
14.3.2.1	SAEs
14.3.2.2	Deaths
14.3 Safety Data Summary figures and tables – 14.3.4 Abnormal Laboratory Value Listing (each patient)	
14.3.4.1	Out of range clinical laboratory
14.3.4.2	Clinical laboratory – haematology
14.3.4.3	Clinical laboratory – clinical chemistry
14.3.4.4	Clinical laboratory – urinalysis
14.3.5	Vital signs
14.3.6	ECG
14.3.7	Prior and concomitant medication and therapies

Clinical Study Reference: IB1001-202

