16.2.6 Adverse event listings	
16.2.6.1	Adverse events
16.2.6.2	AEs leading to discontinuation from the study
16.2.6.3	Vital signs
16.2.6.4	ECG
16.2.6.5	Prior and concomitant medication and therapies

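### The SAP's AE overview row omits AE-related stops of study drug in patients who stay on study, and the treatment-discontinuation count promised in the protocol has no stated place in disposition

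*SAP*

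**What the plan says.** **Protocol.** Section 4.3 lets the physician withdraw a patient either from the study or from the drug. It continues: "Patients who discontinue study drug prior to completing the full treatment period, should be asked to complete the remaining study visits as far as possible". Patients unwilling to do so are offered an early termination visit. Section 6.2.1 keeps recording adverse events in patients who are off treatment but still on study. Section 8.1.1 states: "The number of patients discontinuing treatment, together with the primary reason for discontinuation will be presented". Section 8.1.1 of the Extension (Appendix 6) repeats that commitment, and Section 4.2 of the Extension applies the Parent withdrawal policy.

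**SAP, adverse events.** The overview table in 5.7.1 ends with "any mild/moderate/severe TEAE, any related/unrelated TEAE, any serious AE, and any TEAE leading to study discontinuation". For the tables by system organ class and preferred term, the wording changes: "Similar tables will be created for TEAEs leading to premature discontinuation, SAEs and deaths, if applicable". Table 14.3.1.5 is titled "Treatment emergent adverse events leading to premature discontinuation", and Table 14.3.1.9 gives the same by cycle. Listing 16.2.6.2 is titled "AEs leading to discontinuation from the study", as is Extension Listing 16.2.6.7. SAP 6.7 carries the 5.7 approach into the Extension.

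**SAP, disposition.** Section 5.5.4 summarises included, randomised, treated and completed patients, and then "the frequency and percentage per reason for non-completion will be added". Section 6.5.4 does much the same for the Extension. Neither has a category for patients who discontinued treatment.

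**SAP, listings.** The listing of all adverse events includes action taken (5.7.1), and first and last dosing dates are listed per patient (5.8.2).

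**The concern.** Stopping the drug and leaving the study are different events in this protocol, and drug stoppers are encouraged to remain on study. A tolerability row defined by leaving the study misses exactly those who do as asked. The better sites follow Protocol 4.3, the fewer AE-related drug stops that row can show.

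Safety and tolerability is a secondary objective of both phases. In a single-arm trial with no comparator, the proportion of patients who stopped the drug because of an adverse event is one of the first figures a reader looks for. Protocol 8.1.1 also commits to a count of treatment discontinuations with reasons. The SAP does not specify that count, and SAP Section 7, which lists changes from the protocol, does not mention it.

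**Working it through.** The plan states no figure for this point, so the check is a comparison of text. Take a hypothetical patient who permanently stops IB1001 early in the treatment period because of an adverse event and then attends every visit through Visit 6.

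| Output | Is the AE-related drug stop shown? | Reason |
|---|---|---|
| AE overview, Table 14.3.1.1 (SAP 5.7.1) | No | The row requires study discontinuation |
| Listing 16.2.6.2 | No, by its title | It covers discontinuation from the study |
| Tables 14.3.1.5 and 14.3.1.9 | Undetermined | Premature discontinuation is not defined as drug or study |
| Disposition summary (SAP 5.5.4) | Undetermined | No treatment-discontinuation category; depends on whether the patient counts as completed |
| TEAE tables by class and term, severity, relationship, cycle | The event is shown, its link to the drug stop is not | All TEAEs in the safety set are tabulated |
| All-AE listing and dosing listing | Possibly, patient by patient | Action taken and last dose date are listed |

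**Completion in the Parent study.** Protocol 3.3 requires all phases to be completed, including Visit 6. The treatment period is one of the three phases in Protocol 3.1.2, and Protocol 4.3 describes drug stoppers as not having completed that period in full. The patient could be classed either way. If classed as a non-completer, the reason appears in disposition. If classed as a completer, it does not.

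**Completion in the Extension.** Section 3.3 of Appendix 6 defines completion by attending all routine visits through Visit 12. On that definition a drug stopper who attends them all is a completer, and no reason would be shown.

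**The protocol count.** SAP 5.5.4 and 6.5.4 contain no count of patients discontinuing treatment. This gap does not depend on how any other term is read.

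**Scale, by assumption.** The documents give no rate of AE-related drug stops. Taking about 39 enrolled patients (SAP 2.4.1) and assuming all are dosed:

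- One such patient: 1/39 = 2.6%. Three: 3/39 = 7.7%.
- With a true AE drug-stop rate r, and a share s of those patients staying on study, the expected number shown in the overview row is 39 × r × (1 − s). For r = 5%, 10% and 15%, the expected true numbers are 1.95, 3.9 and 5.85. With s = 0.5 the row shows about 0.98, 1.95 and 2.92. With s = 1 it shows none.
- Were the row to read 0/39, a reader could infer a rate below 1 − 0.05^(1/39) = 7.4% (one-sided 95% exact bound), although that zero would count only study withdrawals.

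For the Extension, with the 20 patients assumed in SAP 2.4.2, each such patient would be 1/20 = 5%.

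**The case against.** The case for leaving the SAP alone has several sound parts.

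- **The events are not lost.** Every TEAE in treated patients is tabulated by class, term, severity, relationship and cycle. Only the link to the drug stop is at risk. This stands.
- **The undefined term may already cover drug stops.** SAP 5.7.1 uses different words for the overview row and for the detailed tables, so premature discontinuation could mean stopping treatment. A listing title is not a definition, and the table templates are in a separate document. This stands as a possibility. If it is the intended meaning, Tables 14.3.1.5 and 14.3.1.9 would disagree with the overview row and with Listing 16.2.6.2, so a definition is needed either way.
- **Drug stoppers may leave anyway.** The request to stay is qualified, and those unwilling go to an early termination visit. They would then appear as study discontinuations. This limits the number affected but does not remove the gap for those who stay.
- **The trial is small.** With about 39 patients, a reader can go through action taken, dosing dates and the per-patient disposition listing. That allows recovery, provided the field records drug discontinuation, but it does not supply the summary count with reasons in Protocol 8.1.1.
- **The SAP never says it drops that count**, and it states that it agrees with protocol version 7.0. It is fair to call this an omission, not a deliberate substitution.

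A reader might infer that AE-related drug stops will be missing from every tolerability and disposition table. The documents do not support that. It would require reading the undefined term as study discontinuation and treating every Parent-study drug stopper as a completer, and neither is settled by the text.

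**Conclusion.** The concern holds in a limited form. An AE-related drug stop in a patient who remains on study is outside the AE overview row and outside Listings 16.2.6.2 and 16.2.6.7 as titled. It may be outside the disposition summary, and its place in the premature-discontinuation tables is undetermined. The protocol's count of patients discontinuing treatment by primary reason is not specified in the SAP for either phase.

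This goes beyond missing detail, because applying the overview row as written understates AE-related drug stops whenever such a patient stays on study. It affects no efficacy analysis, error rate or analysis population. The size is unknown: about 2.6 percentage points per patient on the assumption of 39 treated. The ranges shown illustrate scale and do not predict how many such patients there will be. In particular, a reported 0/39 would arise from this gap only if no patient left the study because of an adverse event, and nothing in the documents says that will happen.

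**What to change.** 1. In SAP 5.7.1 and 6.7, and in the overview tables, report TEAEs leading to permanent discontinuation of study drug in one row and TEAEs leading to study withdrawal in another.
2. Define premature discontinuation in Tables 14.3.1.5 and 14.3.1.9, and in Extension Tables 14.3.1.14 and 14.3.1.18, as discontinuation of study drug.
3. Align Listings 16.2.6.2 and 16.2.6.7 with that definition, with a flag for whether the patient also left the study.
4. Add to SAP 5.5.4 and 6.5.4 the number of patients discontinuing treatment by primary reason, split into those who remained on study and those who left, as Protocol 8.1.1 requires for both phases.
5. Confirm against the CRF that the action-taken field records permanent drug discontinuation. The SAP names the field but not its response options.

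The cost is minor wording and table-shell work if the field is adequate. Reported tolerability may look slightly less favourable.

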2 STUDY INFORMATION

2.1 Study Objectives

2.1.1 Parent study

Primary Objective

The primary objective is to evaluate the efficacy of N-Acetyl-L-Leucine based on blinded raters' clinical impression of change in severity (CI-CS) in the treatment of GM2 Gangliosidosis.

Secondary Objectives

The secondary objectives are:

- To assess the clinical efficacy of N-Acetyl-L-Leucine on symptoms of ataxia, functioning, and quality of life for patients with GM2 Gangliosidosis.
- To evaluate the safety and tolerability of N-Acetyl-L-Leucine at 4 g/day in patients with GM2 Gangliosidosis, including patients aged ≥18 years in the United States and patients aged ≥13 years in Europe, and weight-tiered doses in patients 6 to 12 years of age in Europe.

Exploratory Objectives

The exploratory objective is:

• To characterize the pharmacokinetics (PK) of N-Acetyl-L-Leucine in patients with GM2 Gangliosidosis.

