2.3 Study medication

2.3.1 Parent study

All patients are to receive N-Acetyl-L-leucine (IB1001) in this single-arm study. The study drug will be taken during a 6-week (42 days + 7 days) treatment period. The patient's dose for the Parent phase will be determined based on their age and weight at Visit 1. During the treatment phase of this study, the dosing of the study drug is as follows:

- Patients aged ≥ 13 years in Europe and aged ≥ 18 years in the United States will take 4 g per day: 2 g in the morning, 1 g in the afternoon, and 1 g in the evening.
- Patients aged 6-12 years weighing 15 to <25 kg will take 2 g per day: 1 g in the morning and 1 g in the evening.
- Patients aged 6-12 years weighing 25 to <35 kg will take 3 g per day: 1 g in the morning, 1 g in the afternoon, and 1 g in the evening.
- Patients aged 6-12 years weighing ≥35 kg will take 4 g per day: 2 g in the morning, 1g in the afternoon and 1 g in the evening (as per patients aged ≥13)

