5.5.2 Demographics

Demographic data at baseline will be summarized for all patients and by the 4 age/weight/dosing groups in tabulations.

Appropriate descriptive statistics for age, height, weight, BMI, ethnic group and sex will be given. The summary will be created for each analysis population separately. Additionally, demographic data will be listed.

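### The safety objective is framed by dose, but no planned safety summary table is split by dose; only the listings carry the dosing group

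*SAP*

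**What the plan says.** SAP 2.1.1, matching Protocol 2.2, states the parent study's safety objective as "To evaluate the safety and tolerability of N-Acetyl-L-Leucine at 4 g/day in patients with GM2 Gangliosidosis". It then specifies the age bounds by region and adds "weight-tiered doses in patients 6 to 12 years of age in Europe".

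SAP 2.3.1 sets out four age/weight/dosing groups. Two receive less than 4 g/day: "Patients aged 6-12 years weighing 15 to <25 kg will take 2 g per day", and "Patients aged 6-12 years weighing 25 to <35 kg will take 3 g per day". The other two receive 4 g/day: patients aged 13 or over in Europe (18 or over in the US), and patients aged 6–12 weighing 35 kg or more.

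The SAP uses this grouping elsewhere. SAP 5.5.2 says "Demographic data at baseline will be summarized for all patients and by the 4 age/weight/dosing groups in tabulations", and does so for each analysis population. SAP 5.5.3 makes the grouping a key subgroup. SAP 11.4 makes it a key variable of the individual listings.

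For safety, SAP 5.7.1 says "all TEAEs will be tabulated by System Organ Class (SOC) and Preferred Terms (PTs) within each SOC according to the MedDRA terminology list". Further tables cover severity, relationship, discontinuation, serious events and deaths, and these are repeated by treatment and washout cycle. A typical title in SAP 11.3 is "Treatment emergent adverse events by severity grade by treatment cycle". SAP 5.7.2 to 5.7.4 summarise laboratory values, vital signs and ECGs by visit on the safety set. SAP 6.7 carries the same approach into the Extension.

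**The concern.** An objective framed by dose would normally lead to at least one summary by dose. Here the planned percentages describe all treated patients together. That figure is not the rate at 4 g/day, because patients on 2 or 3 g/day are in the denominator. Nor is it the rate in the weight-tiered children, who may be a small part of the total.

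Two things are at stake. An event concentrated in the lower-dose children would look uncommon in the pooled table. And an event not seen at all would come with a pooled upper bound tighter than the children's own data support.

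**Working it through.** **1. Does any planned safety summary split by dose?** The plan states no figure for safety by dose, so there is none to reproduce. The check is a reading of each output.

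- *TEAE tables (SAP 5.7.1; tables 14.3.1.1 to 14.3.1.9 in SAP 11.3):* overall, SOC/PT, severity, relationship, discontinuation, cycle. No dose split.
- *AE incidence rates (SAP 5.7.1):* per cycle, with all treated patients in the denominator. No dose split.
- *Laboratory, vital signs, ECG (SAP 5.7.2 to 5.7.4):* per visit. No dose split.
- *Extension (SAP 6.7 and 12.3):* the same pattern.
- *Subgroup displays (SAP 5.6):* these use the dosing group, but they cover the primary and secondary efficacy endpoints on the mITT only. Safety endpoints are defined separately in SAP 4.1.5. In SAP 11.3 many efficacy titles specify subgroups and no safety title does.
- *Listings (SAP 11.4 and 12.4):* adverse-event and laboratory listings carry the dosing group for each patient.

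**2. How far can a pooled rate differ from a group rate?** Inputs: planned enrolment of about 39 (SAP 2.4.1). The number k on 2 or 3 g/day is **not in the documents**; 9 is assumed for illustration, with a range of 2 to 12.

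Three events, all in the k lower-dose patients:
- Pooled: 3/39 = 7.7%, whatever k is.
- In the group: 3/4 = 75%, 3/6 = 50%, 3/9 = 33%, 3/12 = 25%.

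Six events, all at 4 g/day, with k = 9 and so 30 patients at that dose:
- 6/30 = 20.0% at that dose, against 6/39 = 15.4% pooled. The distortion on the 4 g/day side is modest.

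Illustrative true rates of 50% in the k patients and 10% in the rest give a pooled rate of (0.5k + 0.1(39 − k))/39:
- k = 2: 4.7/39 = 12.1%.
- k = 9: 7.5/39 = 19.2%.
- k = 12: 8.7/39 = 22.3%.
- The pooled table shows neither true rate.

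**3. What does zero events exclude?** The one-sided 95% upper bound is 1 − 0.05^(1/n).

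| n | Upper bound |
|---|---|
| 39 (all) | 7.4% |
| 30 | 9.5% |
| 12 | 22.1% |
| 9 | 28.3% |
| 6 | 39.3% |
| 2 | 77.6% |

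**4. Would the four existing groups alone give the 4 g/day rate?** No. Two of the four receive 4 g/day, so a combined column is needed. The heavier 6–12 group belongs to both exposures named in the objective: it is weight-tiered and it receives 4 g/day. The four groups do not overlap, so counts add across them.

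**The case against.** The strongest reply is that the information is already there. The listings give each event with the patient's dosing group, and the safety-set demographics table gives the group denominators. With about 39 patients, anyone can count. That stands as far as it goes: the rates are recoverable. But a hand count from listings is not a planned summary.

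Second, the SAP never says that doses are pooled. Table layout is left to a separate template document (SAP 10.4 and 11.1), which was not available, and tables may be split if the data call for it. That is fair. A reader might infer that the SAP rules out a dose split; it does not. It simply does not commit to one.

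Third, the objective can be read as one safety question about one age- and weight-adapted regimen, which the overall rate answers. This reading is possible, and neither document promises a rate per dose. But the objective does name the doses, and the SAP treats the dosing group as worth tabulating for demographics and efficacy.

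Fourth, cells will be small. With two lower-dose patients, zero events excludes only rates above 77.6%. That limits what the columns can show and rules out inference from them. It also shows that the pooled bound of 7.4% should not be read as applying to the lower-dose children.

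A reader might also infer that pooling hides the highest exposure per kilogram, in the smallest children. The documents do not support that. Patients aged 13 or over in Europe have no weight tier, and the only weight floor is 15 kg. A 25 kg patient in that group would receive 4000/25 = 160 mg/kg/day, more than the 2000/15 = 133 mg/kg/day of a 15 kg child on 2 g. Dosing group is a poor proxy for exposure per kilogram.

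**Conclusion.** The gap is real and modest. The safety objective names doses, and no planned safety summary table reports by dose. The rates are not lost, because listings and safety-set denominators allow a hand count.

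The size cannot be fixed from the documents because group sizes are not given. Under the assumed 9 of 39, three events confined to the lower-dose patients read as 33% in the group and 7.7% pooled, and the zero-event bounds are 28% and 7.4%. With fewer lower-dose patients both contrasts widen; with 12, they narrow to 25% against 7.7% and 22.1% against 7.4%.

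Nothing here touches the primary endpoint or any test. A reader might infer that the study cannot describe safety by dose; the accurate statement is that it can, but does not plan to tabulate it.

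**What to change.** In the parent study, on the safety set, add descriptive columns to the TEAE overview, TEAE by SOC/PT, related TEAE, serious TEAE, laboratory and ECG tables in SAP 5.7 and 11.3:

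- each of the four assigned age/weight/dosing groups;
- a combined 4 g/day column (aged 13 or over in Europe or 18 or over in the US, plus aged 6–12 weighing 35 kg or more);
- a combined 2–3 g/day column;
- Total.

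State that the groups follow assigned dose, and flag patients whose dose was reduced. Protocol 5.3 allows reductions of up to one-half, and SAP 5.8.2 already plans to use actual dose for compliance if it is collected.

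For the Extension, use the Visit 7 group already defined in SAP 6.5.2, and list events that occur after a change of dose group. Grouping by dose at event onset would need a new derived variable and a denominator rule for patients who change group. It would also rest on age data that SAP 10.1 says are not collected in the Extension.

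Cost: the parent-study columns use a grouping that already exists and need no new data collection or testing. The tables become wider, and some cells will hold only a few patients, so a footnote should say that they are descriptive.

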To address the study delays due to Covid-19 in reference to AE occurrences, AE incidence rates will also be determined per study cycle (treatment cycle and washout cycle). Incidence rate of adverse events is defined as the number of adverse event cases per patient-year(s). The calculation of the incidence rate is the number of cases (i.e. patient with an AE) divided by the sum of the follow-up time of all patient at risk (which will be all subjects receiving treatment). This calculation is accomplished as follows:

- Denominator: ∑p_i × t_i, where p_i = patient i and t_i= treatment duration of patient i in years (total # days divided by 365.25), where treatment duration is determined based on first and last (dose) date.
- Numerator: the total number of cases (note: a single patient can be counted more than once if the AE occurs on separate occasions)
- Incidence rate=numerator/denominator

The use of this measure implies the assumption that the incidence rate is constant over different periods of time. Since the calculation is done per cycle, the denominator (patient-years) is also determined per cycle, based on the patients available within that cycle.

Clinical Study Reference: IB1001-202

Separate listings will be created for SAEs and deaths, if applicable. The SAF population is used for the AE presentations.

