6.7 Safety and tolerability evaluation

The safety and tolerability evaluation for the extension study is similar to what is described for the Parent study (see Section 5.7), with the remark that the evaluation is limited to the Extension phase only and Visit 7 is considered the baseline. For the AE presentation per treatment cycle, the cycles for Extension phase are as follows:

- Treatment cycle Extension phase I: the period between start of first treatment at Visit 7 and 24 hours after last dose at Visit 9.
- Washout cycle Extension phase I: starts 24 hours after last dose at Visit 9 until and includes Visit 10.
- Treatment cycle Extension phase II: the period between start of first treatment at Visit 10 and 24 hours after last dose at Visit 12.
- No washout cycle is defined for Extension phase II.

Note that for those patients that do not transition seamlessly to the Extension phase, additional prior medication/adverse events may be collected at the start of the Extension phase, and these will be presented separately from the prior medication/adverse events of the Parent phase.

Physical examination, which is collected twice during the Extension phase, will be presented as follows: general physical examination data will be tabulated and listed per visit. The summary table will include number/percentage of patients with normal or abnormal observations and NCS/CS frequencies/percentages for abnormal observations per visit.

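### The only person-time formula for adverse event incidence rates uses dosing time, which cannot measure the washout cycle and conflicts with the text around it; separately, the numerator is defined two ways

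*SAP*

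**What the plan says.** SAP 5.7.1 introduces incidence rates, separately for the treatment and washout cycles, to allow for study delays caused by COVID-19. It describes the denominator in three ways.

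- In prose, the rate is "the number of cases (i.e. patient with an AE) divided by the sum of the follow-up time" of all patients at risk.
- In the formula, each patient contributes t_i, a treatment duration in years, where "treatment duration is determined based on first and last (dose) date".
- In the closing sentence, "the denominator (patient-years) is also determined per cycle, based on the patients available within that cycle".

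The prose ties a case to a patient with an AE. The formula's numerator bullet instead notes that "a single patient can be counted more than once if the AE occurs on separate occasions".

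The same section already sets the windows for the Parent Study. The treatment cycle runs from the first treatment at Visit 2 until 24 hours after the last dose at Visit 4. The washout cycle runs from that point through Visit 6. SAP 6.7 carries the safety methods into the Extension Phase with its own windows, for example "Washout cycle Extension phase I: starts 24 hours after last dose at Visit 9 until and includes Visit 10".

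The Extension Phase table list (SAP 12.3) includes an incidence-rate table, 14.3.1.19. The Parent Study list (SAP 11.3) has none.

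**The concern.** A rate per patient-year is interpretable only if the time in the denominator is the time in which the counted events could occur. The washout window opens 24 hours after the last dose, so a duration bounded by dose dates contains none of it. SAP 5.8.2 uses the same two dates to define the total dosing period, which supports reading t_i as dosing time. The SAP gives no formula for washout days.

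The table is meant to remove the effect of unequal cycle lengths. With dosing time under the washout events, it would bring that inequality into the rate instead. In a single-arm study the on-drug versus off-drug contrast is the only internal comparison of AE rates, so an error in one of the two rates distorts the comparison directly.

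The numerator is a separate problem. Patients with an event and number of events are different statistics, and the section supports both.

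**Working it through.** The documents state no incidence rate, event count or person-time total, so there is no planned figure to reproduce. The check is of the formula.

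**Inputs**

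- Parent Study dosing: 42 days (+7), Protocol 3.1.2.2. Washout: 42 days (+7), Protocol 3.1.2.3.
- Visits 4 and 6 may both be postponed (Protocol 3.1.2.5.2). Dosing continues to a postponed Visit 4, with no upper limit given (Protocol 5.3).
- Extension Phase treatment period I: 365 days (±14). Extension washout: 42 days (+14). Both from SAP 2.2.2.

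**Formula.** Let E be the number of washout events.

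- Rate with dosing time as denominator = E / (sum of dosing days / 365.25)
- Rate with washout time as denominator = E / (sum of washout days / 365.25)
- Ratio of the first to the second = washout days / dosing days

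E cancels, so the ratio does not depend on the number of events. The 24-hour offset between the cycles is ignored; it changes a 42-day cycle by about 2% (41/42 = 0.976).

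| Setting | Dosing days | Washout days | Reported / correct washout rate |
|---|---|---|---|
| Parent Study, planned | 42 | 42 | 1.00 |
| Parent Study, dosing at end of window | 49 | 42 | 0.857 |
| Visit 4 postponed (assumed) | 84 | 42 | 0.50 |
| Visit 4 postponed (assumed) | 126 | 42 | 0.333 |
| Parent Study, washout at end of window | 42 | 49 | 1.167 |
| Visit 6 postponed (assumed) | 42 | 84 | 2.00 |
| Extension Phase I, planned | 365 | 42 | 0.115 |

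The Extension result is an understatement of 365/42 = 8.7-fold. Across the visit windows it runs from (365 − 14)/(42 + 14) = 351/56 = 6.3-fold to (365 + 14)/42 = 379/42 = 9.0-fold. With washout time in the denominator, every ratio in the table is 1.00.

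**Illustration with assumed counts.** Take 30 patients, a 42-day washout and 10 washout events. Person-time is 30 × 42 / 365.25 = 3.450 patient-years and the rate is 10 / 3.450 = 2.90 per patient-year. If dosing had lasted 84 days and that time were used, person-time would be 6.899 patient-years and the rate 1.45.

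**Numerator.** Suppose the same 10 events occurred in 6 patients. Counting events gives 2.90; counting patients gives 6 / 3.450 = 1.74. The factor is 10/6 = 1.67, the mean number of events per affected patient. It is unrelated to the choice of denominator.

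**The case against.** The strongest reply is that the section, read as a whole, does not tell anyone to put dosing time under washout events. The prose denominator is follow-up time. The closing sentence has patient-years determined per cycle, and patient-years include time as well as headcount. The word dose stands in brackets, so the phrase could mean the first and last date of the cycle. The windows for every cycle are already in the SAP, and a careful programmer could use them. The display carries no test or decision rule. Per-cycle frequencies and dated AE listings are planned as well, so a wrong rate could be found and recomputed.

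Much of this stands. A reader might infer that the plan instructs dosing time for washout and so makes off-drug rates look low throughout. The documents do not support that: the wording points in more than one direction, the error can go either way, and at the planned Parent Study durations it is nil. A reader might also link the double numerator to the understatement. It does not cause it.

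What does not stand is that the other wording settles the matter. The per-cycle sentence names the patients to be included but gives no start or end date for their time. Follow-up time is defined in the SAP only for the disposition listings, and those definitions span treatment and washout together. In SAP 5.5.4 it runs from first dose to the end of the Parent phase, planned at 84 days. In SAP 6.5.4 it runs from the first Extension dose to the end of the Extension Phase or withdrawal, planned at 767 days for a patient who reaches Visit 12. Borrowing those would understate the washout rate by 84/42 = 2.0-fold and 767/42 = 18.3-fold. The reading that gives the right answer has to be inferred.

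**Conclusion.** The concern holds as an internal inconsistency. SAP 5.7.1 asks for a washout rate, gives one explicit person-time formula that cannot measure washout time, and surrounds it with wording that points elsewhere.

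The size is conditional on the formula being applied as written. It is 8.7-fold too low at the planned Extension durations, nil at the planned Parent Study durations, too low if a postponed Visit 4 lengthens dosing alone, and too high if a postponed Visit 6 lengthens washout alone. The Extension figure comes from the planned schedule, not from COVID-19 delay; the prolonged Parent Study durations in the table are assumptions. The possible error is largest in the Extension Phase, the only phase whose table list includes the rate.

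The numerator conflict is a separate defect and holds without that condition. The opening definition and the formula bullet fit a count of events; the bracketed gloss on patients is what conflicts.

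The consequence is limited to a descriptive safety display. It should be corrected, but the primary endpoint is not affected.

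**What to change.** 1. In SAP 5.7.1, define t_i as time in the cycle. Treatment: from first dose to 24 hours after last dose. Washout: from that point to the end-of-washout visit (Visit 6) or withdrawal, if earlier.
2. State in SAP 6.7 that the same rule applies with the Extension Phase windows already listed there, so that Extension washout time ends at Visit 10 or withdrawal.
3. Define the numerator as the number of events and delete the bracketed gloss that equates a case with a patient. This agrees with the formula bullet and with the constant-rate assumption stated beside it. If patients with a first event are preferred, person-time must be censored at that event.
4. Add an incidence-rate table to the Parent Study list in SAP 11.3, to match 14.3.1.19 in SAP 12.3.

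The cost is a few sentences and one table entry. Dosing and visit dates are already to be listed per patient (SAP 5.8.1 and 5.8.2), so no new data are needed.
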